9.2. Adverse Events

Adverse events tables will summarize the number and proportion of patients with an event by SOC and PT for the Safety Population and Ex11 Safety Population. All tables will only include treatment emergent AEs (TEAEs), where TEAEs are defined as any AE which occurs after the administration of the first dose of study drug and through 30 days after the last dose of study drug or the day before the start of subsequent new anticancer drug therapy, whichever occurs first. Drug-related AEs reported after 30 days after the last dose of study drug will also be considered TEAEs. Listings will include all reported AEs, flagging events that were TEAEs. In the case of missing start and/or stop date, non-missing date parts will be used to determine if an AE is treatment-emergent or not. An AE will be categorized as TEAE if a determination cannot be made using the non-missing date parts as to when the event occurred relative to study drug administration. Adverse event toxicity grade will be classified using NCI-CTCAE Version 5.0 criteria. For incidence summaries, a missing toxicity grade of a TEAE will be conservatively imputed as severe; for a TEAE missing causal relationship to study treatment, a causality of "related" will be assigned. Listings will include all reported AEs, flagging events that were TEAEs and displaying missing start/stop dates, severity grades and causalities as they were entered in the clinical database.

An overall summary of the number of patients with TEAEs will be presented, including the number and percentage of patients with any TEAEs, serious TEAEs (TESAE), drug-related TEAEs and TEAEs leading to dose modification, treatment discontinuation, and death.

The number and percentage of patients reporting TEAEs in each treatment arm will be tabulated by SOC and PT; by PT; by SOC, PT, and maximum severity. If a patient has multiple occurrences of the same SOC and PT, then the patient will be counted only once for the SOC and PT using the most severe occurrence for the summarization by maximum severity. Presentation by SOC and PT will display SOC sorted alphabetically and PT by descending frequency based on frequencies observed in the ripretinib arm.

TEAEs and drug-related TEAEs will be summarized by SOC and PT, PT in descending frequency. TEAEs and drug-related TEAEs leading to dose modification, study treatment discontinuation, and TESAEs leading to death will be summarized by SOC, PT, and treatment arm.

Adverse events of special interest (AESI) are serious or nonserious AEs of scientific and medical concern specific to study drug, for which ongoing monitoring and immediate notification by the Investigator to the Sponsor is required. AESIs will be flagged on the eCRF by the investigator. The following AEs are considered AESIs: squamous cell carcinoma (SCC) of skin, actinic keratosis, and keratoacanthoma.

The number and percentage of patients by treatment arm with the following categories of TEAEs will be summarized in tables by SOC and preferred term:

- Any AE
- Any AE by maximum severity grade

CONFIDENTIAL Page 25 of 29

- Any AE by maximum severity grade 1/2, 3/4, and 5
- Any drug-related AE
- Any SAE
- Any drug-related SAE
- Any AE leading to dose modification (dose reduction and dose interruption) or treatment discontinuation
- Any drug-related AE leading to dose modification or treatment discontinuation
- Any AESI
- Any AESI by maximum severity grade
- Any drug-related AESI
- Any fatal AE

9.3. Deaths

The number of patients with reported death and cause of death will be summarized by treatment arm for Ex11 ITT and AP ITT populations.

- Summary of all deaths by cause of death (Progressive disease, Adverse event, Other)
- Summary of all deaths ≤ 30 days of last dose by cause of death (Progressive disease, Adverse event, Other)
- Summary of all deaths > 30 days of last dose by cause of death (Progressive disease, Adverse event, Other)

A data listing of all deaths will be provided.

9.4. Eastern Cooperative Oncology Group Performance Status

The Eastern Cooperative Oncology Group (ECOG) Performance Status Assessments will be summarized as a categorical variable at each visit.

9.5. Clinical Laboratory Data

Clinical laboratory measurements will be collected from screening until the end of treatment visit (within 7 days of the last dose). Laboratory values will be graded for severity according to the National Cancer Institute Common Terminology Criteria for Adverse Events (NCI-CTCAE), Version 5.0.

Table 3: Safety Laboratory Tests

Serum Chemistry	Hematology	Urinalysis
Blood urea nitrogen	Hemoglobin	Urine protein
Creatinine	 Mean corpuscular hemoglobin 	Urine blood
Sodium	 Mean corpuscular hemoglobin 	Specific gravity
Potassium	concentration	Urine ketones
Calcium	Mean corpuscular volume	Urine glucose

CONFIDENTIAL Page 26 of 29

Magnesium	Hematocrit
Phosphorus	Platelets
Total and direct bilirubin	Leukocytes
Alkaline phosphatase	Reticulocytes
Aspartate aminotransferase	Differential (absolute):
Alanine aminotransferase	Eosinophils
Lactate dehydrogenase	Basophils
Total protein	Neutrophils
Albumin	• Lymphocytes
Creatine Phosphokinase	Monocytes
Globulin	
Triglycerides	Coagulation Studies (for patients
Lipase	taking anticoagulants)
Amylase	Activated partial thromboplastin
TSH	time
T3	Prothrombin time
T4	International Normalized Ratio

Assessments will be summarized by time point utilizing continuous descriptive statistics as appropriate. In addition, the numeric changes from baseline will be summarized for continuous parameters. For categorical parameters, the number and percentage of patients with assessment will be displayed.

Changes in severity from baseline will be summarized by the maximum shift in CTCAE severity grade from baseline to post baseline.

9.6. Vital Signs

Temperature, heart rate, respiratory rate, and blood pressure will be summarized overall by time point utilizing continuous descriptive statistics. In addition, the change from baseline will be summarized for continuous parameters. For categorical parameters, the number and percentage of patients with assessment will be displayed.

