**Table 1: Schedule of Assessments**

Assessments / Procedure 	Screening 	Cycle 1			Cycle 2		Cycles ≥3		EOT Visit (within 7 days after last dose)	Safety Follow Up 30 Days Post Last Dose (+5 days)	Overall Survival Follow Up  (every 3 months ±1 month)
		1 (Baseline)	15 (±1 day)	29 (±1 day)	1 (±3 days)	29 (±3 days)	1 (±3 days)	29 (±3 days)			
Site Visit	X	X	X	X	X	X	X		X		
Remote Questionnaire Completion 								X 			
Phone Call										X	X
Informed Consent	X										
Inclusion/Exclusion Criteria	X										
Medical and Cancer History	X										
Prior Medications/Procedures 	X										
Pregnancy Test 	X	X			X		X		X		
Randomization 		X									
Clinical Laboratory Tests											
Hematology	X	X	X	X	X	X	X		X		
Serum Chemistries	X	X	X	X	X	X	X		X		
Coagulation 	X	X	X 	X	X	X	X		X		
Urinalysis	X	X			X		X 		X		
TSH, Total T3 and Total T4	X	X					X 		X		
Physical Examination	X	Examinations will be driven by clinical findings and/or patient complaints									
ECOG PS 	X	X	X	X	X	X	X		X		
Vital Signs and weight 	X	X	X	X	X	X	X		X		
Height	X										
12-lead ECG 	X	X			X		X		X		
Echocardiogram/MUGA 	X						X 		X		
Dermatologic Examination 	X						X 		X		
Adverse Event Reporting		Continuous from signing informed consent through safety follow up									
Concomitant Medications/Procedures		Continuous from on or after the first dose of study drug through safety follow up									

Assessments / Procedure 	Screening 	Cycle 1			Cycle 2		Cycles ≥3		EOT Visit (within 7 days after last dose)	Safety Follow Up  30 Days Post Last Dose (+5 days)	Overall Survival Follow Up  (every 3 months ±1 month)
		1 (Baseline)	15 (±1 day)	29 (±1 day)	1 (±3 days)	29 (±3 days)	1 (±3 days)	29 (±3 days)			
EORTC QLQ-C30 	X	X	X	X	X	X	X	X	X		
EQ-5D-5L 		X	X	X	X	X	X	X	X		
Healthcare Utilization		X			X		X		X		
PRO-CTCAE Questions 46 and 47 		X	X	X	X	X	X	X	X		
GP5 questions from FACT-G 	X	X	X	X	X	X	X	X	X		
DLQI 	X	X	X	X	X	X	X	X	X		
Study Drug Administration 		X	X	X	X	X	X	X			
Study Drug Dispensation		X			X		X				
PK Sampling 		X	X		X		X 		X		
Pharmacogenomics 		X									

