**Table 3: Summary of Treatment Emergent Adverse Events (TEAE) that Occurred in ≥ 10% GIST Patients @ 150 mg QD (n=114)**

System Organ Class	Subjects n=114 (%)				
	All	1	2	3	4
Alopecia	48 (42.1)	34 (29.8)	14 (12.3)		
Fatigue	45 (39.5)	32 (28.1)	13 (11.4)		
Myalgia	41 (36.0)	35 (30.7)	6 (5.3)		
Constipation	35 (30.7)	27 (23.7)	8 (7.0)		
Hand-Foot-Syndrome	30 (26.3)	25 (21.9)	4 (3.5)	1 (0.9)	
Rash	26 (22.8)	25 (21.9)	1 (0.9)		
Nausea	25 (21.9)	22 (19.3)	3 (2.6)		
Decreased appetite	22 (19.3)	15 (13.2)	6 (5.3)	1 (0.9)	
Lipase increased	21 (18.4)	7 (6.2)	3 (2.6)	9 (7.9)	2 (1.8)
Diarrhoea	19 (16.7)	15 (13.2)	2 (1.8)	2 (1.8)	
Abdominal pain	17 (14.9)	11 (9.6)	4 (3.5)	2 (1.8)	
Weight decreased	17 (14.9)	14 (12.3)	3 (2.6)		
Arthralgia	16 (14.0)	15 (13.2)	1 (0.9)		
Hypertension	15 (13.2)	3 (2.6)	9 (7.9)	3 (2.6)	
Headache	14 (12.3)	13 (11.4)	1 (0.9)		
Vomiting	14 (12.3)	9 (7.9)	5 (4.4)		
Pain in extremity	14 (12.3)	14 (12.3)			
Dyspnoea	13 (11.4)	9 (7.9)	3 (2.6)	1 (0.9)	
Muscle spasms	13 (11.4)	11 (9.6)	2 (1.8)		
Anaemia	12 (10.5)	5 (4.4)	3 (2.6)	4 (3.5)	
Dry skin	12 (10.5)	11 (9.6)	1 (0.9)		

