**Table 7: DCC-2618 Dose Modifications and Management of Hypertension**

Toxicity Grade	Management Guideline*
Grade 1 Prehypertension (systolic BP 120-139 mm Hg or diastolic BP 80-89 mm Hg)	Continue BP monitoring Continue DCC-2618 at the current dose level
Grade 2 Systolic BP 140-159 mm Hg or diastolic BP 90-99 mm Hg Or Symptomatic increase by > 20 mm Hg (diastolic) or to > 140/90 mm Hg if previously within normal limits	Treat BP to achieve diastolic BP $\leq$ 90 mmHg and or systolic BP $\leq$ 140 mmHg 
 
• If BP was previously within normal limits, start antihypertensive monotherapy
 
• If patient is already on antihypertensive medication, titrate dose up
 
 Continue the DCC-2618 at the current dose level Hold DCC-2618 if symptomatic increase by 20 mmHg (diastolic BP) until symptoms resolve and diastolic BP $\leq$ 90 mmHg On resuming DCC-2618, continue at the same dose level
Grade 3 Systolic BP <math>\geq</math> 160 mm Hg or diastolic BP <math>\geq</math> 100 mm Hg Or More than 1 drug or more intensive therapy than previously indicated	Treat to achieve diastolic BP $\leq$ 90 mmHg and or systolic BP $\leq$ 140 mmHg 
 
• Start antihypertensive medication and/or
 
• Increase current antihypertensive medication and/or
 
• Add an additional antihypertensive medication
 
 If symptomatic, hold DCC-2618 until diastolic BP $\leq$ 90 mmHg and/or systolic BP $\leq$ 140 mmHg, and symptoms resolve On resuming DCC-2618, continue at the same dose level If BP is not controlled with addition of a new or more intensive therapy, reduce DCC-2618 by 1 dose level If Grade 3 hypertension recurs despite DCC-2618 dose reduction and antihypertensive therapy, reduce the DCC-2618 by 1 additional dose level
Grade 4 Life-threatening consequences (e.g. malignant hypertension, transient or permanent neurologic deficit, hypertensive crisis)	Treat BP per institutional guidelines Permanently discontinue DCC-2618

BP=blood pressure

\*If BP remains controlled for at least 28 days, DCC-2618 dose re-escalation is permitted at the Investigator's discretion.

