### 6.11.3. Vital Signs, and Weight and Height

Vital sign measurements, height, and weight will be performed according to Table 1 (schedule of assessments). Vital sign measurements will include sitting blood pressure, pulse, respiratory rate, and body temperature. These will be assessed following a 5-minute rest (seated or supine position).

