3.6. General Analysis Conventions

Continuous data will be summarized using descriptive statistics (number of patients with assessment, mean, median, standard deviation, minimum, and maximum). Categorical data will be summarized using frequencies and proportions. Time-to-event data will be reported in months, and summarized via Kaplan-Meier (KM) methodology using the 25th, 50th (median), and 75th percentiles with associated 2-sided 95% confidence intervals (CIs), and time point survival probabilities with associated 2-sided 95% CIs.

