5. PATIENT DISPOSITION

Patient disposition will be summarized overall and by treatment arm. The number and proportion of patients will be displayed for each population (i.e., Ex11 ITT, AP ITT, Safety, Ex11 Safety, PK, Ex11 PP, and AP PP). The number and proportion of patients in the Safety Population and Ex11 Safety Population who have discontinued from treatment will be summarized by the primary reason for treatment discontinuation. The number and proportion of patients in the Ex11 ITT population and AP ITT population who have discontinued from the study will be summarized by the reason for study discontinuation as well.

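### SAP 9.6 plans no by-arm count of patients by worst post-baseline blood pressure and no post-baseline weight summary, although both are measured throughout treatment

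*SAP*

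**What the plan says.** SAP 9.6 covers four vital signs: "Temperature, heart rate, respiratory rate, and blood pressure will be summarized overall by time point utilizing continuous descriptive statistics". It adds: "In addition, the change from baseline will be summarized for continuous parameters". SAP 3.6 defines the statistics: "Continuous data will be summarized using descriptive statistics (number of patients with assessment, mean, median, standard deviation, minimum, and maximum". A further sentence in 9.6 deals with categorical parameters, but none of the four listed is categorical. Protocol 9.8.6.3 is equally general and sets no thresholds.

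Weight is collected on treatment. Protocol 6.11.3 states: "Vital sign measurements, height, and weight will be performed according to Table 1". The row "Vital Signs and weight" in protocol Table 1 is marked at screening, Cycle 1 Days 1, 15 and 29, Cycle 2 Days 1 and 29, Day 1 of each later cycle, and the end-of-treatment visit. In the SAP, weight is listed only among the baseline characteristics in 7.1.

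Neighbouring safety data are handled in more detail. Laboratory values get a maximum shift in CTCAE grade (SAP 9.5). ECG intervals and heart rate get outlier categories by treatment arm (SAP 9.7). LVEF gets a count of Grade 3 decreases (SAP 9.8).

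**The concern.** Comparing the safety profiles of the two drugs is a stated objective (protocol 2.2.2, SAP 2.1.3). Hypertension and "Weight decreased" both exceed 10% in protocol Table 3, and hypertension has its own management table (Table 7). For these two, a reader of the study report will want to know how many patients in each arm crossed a given level on measurement. The planned vital-sign tables do not say.

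The remaining source is adverse event reporting. Under protocol 7.7.1 an abnormal vital sign becomes an adverse event when it is judged clinically significant, and the investigator makes that determination knowing the treatment. Measured values by arm are the natural check on that route.

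**Working it through.** **1. Phase 1 rates (protocol Table 3, n = 114).** Each is k/114.
- Hypertension: 15/114 = 13.2%. Grade 1, 3/114 = 2.6%; Grade 2, 9/114 = 7.9%; Grade 3, 3/114 = 2.6%.
- Weight decrease: 17/114 = 14.9%. Grade 1, 14/114 = 12.3%; Grade 2, 3/114 = 2.6%.

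All match the table.

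**2. Expected numbers in one arm of 213 at those rates.**
- Hypertension: 213 × 15/114 = 28.0, of which Grade 3: 213 × 3/114 = 5.6.
- Weight decrease: 213 × 17/114 = 31.8.

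There are enough patients for a count by category to be informative.

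**3. What a by-visit mean can show.** Assume that a share f of an arm rises by d mmHg and the rest do not change. The arm mean change is f × d. The documents give no value for d, so these are assumed ranges:
- f = 13.2%, d = 15 to 30: 0.132 × 15 = 2.0 to 0.132 × 30 = 4.0 mmHg.
- f = 5%, d = 15: 0.75 mmHg. f = 20%, d = 30: 6.0 mmHg.
- f = 5%, d = 30 gives 1.5 mmHg, and so does f = 10%, d = 15.

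The last line is the useful one. The same mean arises from incidences that differ by a factor of two, so the mean does not give the number affected. The per-visit maximum shows one extreme reading, not how many patients passed a limit.

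**4. Treatment to target.** For ripretinib patients, Table 7 calls for antihypertensive treatment from Grade 2, for example: "If patient is already on antihypertensive medication, titrate dose up". Later readings in affected patients are therefore pulled down. The highest reading that patient had is retained only by a worst-value summary.

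**5. Timing of readings.** Assessments are predose unless stated otherwise (Table 1, footnote 1). On an unmodified sunitinib schedule, Days 1 to 28 are on drug and Days 29 to 42 are off. Scheduled post-baseline readings up to Cycle 7 Day 1 are:
- during dosing, or the day after it ends: Cycle 1 Days 15 and 29, Cycle 2 Day 29 = 3;
- after the two-week break: Cycle 2 Day 1 and Day 1 of Cycles 3 to 7 = 1 + 5 = 6.

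So 6 of 9, and every scheduled in-cycle reading from Cycle 3 on, compares sunitinib after a break with continuously dosed ripretinib. How far pressure changes in the break is not given in the documents. A worst-value summary cannot create later on-drug readings, but it carries the Cycle 1 and 2 readings forward for each patient.

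**6. Weight.** Collection is scheduled throughout treatment, and no post-baseline output is planned. No arithmetic is needed.

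**The case against.** The best reply is that the adverse event tables already do this. Protocol 7.7.1 gives criteria: an abnormal assessment is clinically significant if medical intervention is required or study drug is changed. Ripretinib patients treated under Table 7 meet that criterion, and SAP 9.2 tabulates events by arm, preferred term and maximum severity. This stands, and it means that neither signal is lost. It does not close the gap. The final determination remains the investigator's. Table 7 governs only ripretinib, while sunitinib follows the package insert or institutional guidelines, so the treatment that triggers an event may differ by arm. Table 7 also allows Grade 3 on treatment intensity alone. The concomitant medication table in SAP 9.10 helps only in part, because it includes drugs begun before the first dose.

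Four stronger readings are tempting, and the documents do not support them:
- *Only means are planned, so hypertension cannot be seen.* SAP 3.6 adds the median, SD, minimum and maximum, and 9.6 adds change from baseline. What is missing is a count of patients.
- *The arms are pooled.* The word *overall* in 9.6 invites this, since SAP 5 writes "Patient disposition will be summarized overall and by treatment arm". But protocol 9.8.5.3.2 uses *overall* for EQ-5D-5L and then tests one arm against the other. SAP 9.9 pairs it with location, and SAP 4.2 assigns safety patients to the treatment first received, which would be pointless if arms were combined. The wording is unclear and no more than that.
- *These are established ripretinib effects.* Table 3 lists treatment-emergent events from an uncontrolled Phase 1 study. Neither is an event of special interest, and weight decrease had no Grade 3 or 4 case.
- *Omitting weight breaks a stated endpoint.* Protocol 6.11.3 names weight separately from vital signs, and the safety endpoints in 9.2.2.2.1 do not list it. It is an omission worth repairing and contradicts nothing.

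**Conclusion.** The point holds as a gap in the planned outputs. Measured blood pressure yields no by-arm count of patients by worst value or shift, and measured weight yields no post-baseline result. At Phase 1 rates this concerns about 28 and 32 patients in an arm of 213. Those counts assume that the Phase 1 adverse event rates carry over to this population. The mmHg figures are illustrations on assumed rises and do not carry the conclusion, which rests on the fact that a mean or a single maximum is not an incidence. The timing argument assumes the 4/2 schedule is kept without modification.

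The gap matters because the trial is open label and compares safety profiles. It touches no efficacy conclusion, no alpha and no power, and both events remain visible as graded adverse events.

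**What to change.** In SAP 9.6:
- State that all summaries are by treatment arm.
- Add a shift table from baseline (as defined in SAP 3.4) to maximum post-baseline blood pressure. Use the numeric systolic and diastolic bands already in protocol Table 7, plus a row for values below Grade 1, since Table 7 has none. Classify by the higher of the two bands, and say whether unscheduled readings count. These are reporting categories only.
- Add weight: percentage change from baseline by visit, and maximum loss in pre-specified categories (for example ≥5% and ≥10%).
- Optionally, count patients who newly started an antihypertensive after the first dose, from the concomitant medication data.

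A maximum tends to grow with the number of readings, so print the number of readings per patient or the treatment duration beside these tables.

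The cost is SAP wording and two or three extra tables. No dose or clinical rule, alpha, power or data collection changes.

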9.7. Electrocardiograms

PR, QRS, QT, QTc (ie, QTcB and QTcF) and RR intervals and their change from baseline will be summarized for each treatment arm by scheduled visit. Patients will be categorized into >450, >480, or >500 ms per their maximum post-baseline absolute QTc interval and >30, or >60 ms per their maximum change from baseline QTc interval. Additionally, patients will be classified into the following categories: HR \le 50 bpm and/or decrease from baseline \ge 20 bpm; HR \ge 120 bpm and/or increase from baseline \ge 20 bpm; PR \ge 220 ms and/or increase from baseline \ge 20 ms; QRS \ge 120 ms. The number and percentage of patients in each category will be summarized for each treatment group.

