2.2.2. Treatments and Assignment to Treatments

Approximately 426 patients (213 randomized to ripretinib and 213 randomized to sunitinib) will be randomized in this study at approximately 125 centers globally. Patients will be randomized to receive 150 mg QD of ripretinib or 50 mg of sunitinib in repeated 42-day cycles. Ripretinib will be given continuously and sunitinib will be given continuously for 4 weeks with a 2 week break. Sunitinib dose modifications are allowed per approved package insert or institutional guidelines.

Patients will be treated until they develop progressive disease based on IRR as per mRECIST, experience unacceptable toxicity, or withdraw consent. If the Investigator wishes to end treatment due to local progression based on mRECIST, without confirmation of progression by IRR, or before the independent read results are available, the Investigator must reach out to the Sponsor Medical Monitor to discuss.

Patients will be eligible to receive study drug for up to 2 years. This will be extended by agreement between the Sponsor and Investigator for patients who exhibit evidence of clinical benefit and tolerability to the drug, and who adhere to the study procedures. The study will end following the last patient last visit.

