2.3. Determination of Sample Size

The sample size selection of 426 patients (n=213 ripretinib, n=213 sunitinib) was based on considerations for powering of the primary endpoint, secondary endpoints, detection of rare safety events and overall exposure to ripretinib. Patients will be randomized in a 1:1 ratio of ripretinib versus sunitinib.

Under the assumptions that median progression-free survival (mPFS) is 9 months for ripretinib and 6 months for sunitinib, the HR is about 0.667 for All Patients (AP) PFS (ripretinib vs sunitinib). A total of 262 events will be required to achieve a statistical power of 90% to test the hypothesis of no difference between ripretinib and sunitinib in AP. Accrual of 426 patients (213 in ripretinib and 213 in sunitinib) within 21 months is expected to have 262 PFS events occurred after additional 8 months of follow up. This has accounted for 20% of dropout rate (discontinuation without progressive disease per IRR or death).

It is further assumed that the mPFS is 9 months for patients with a KIT Exon 11 primary mutation (Ex11) in ripretinib and 5 months for KIT Ex11 in sunitinib, the HR is 0.556 for the KIT Ex011 PFS. A minimum of 151 PFS events in KIT Ex11 population have at least 95% power to test the hypothesis of no difference between ripretinib and sunitinib in KIT Ex11 population.

No interim analysis is planned for PFS based on IRR. The final analysis of PFS based on IRR will be performed in the Ex11 ITT population and in the AP ITT population (as defined in Section 4) using the same data cutoff, following the hierarchical testing sequence specified in Section 8.5. This final analysis is planned to occur when at least 151 PFS events in Ex11 ITT population and approximately 262 PFS events in AP ITT population have occurred. The analysis of PFS in Ex11 ITT population and AP ITT population will be based on the actual number of events observed in Ex11 ITT population and AP ITT population, respectively, at the time of final analysis of PFS.

CONFIDENTIAL Page 9 of 29

At the time of final analysis of PFS by IRR, ORR by IRR and OS in Ex11 ITT and AP ITT will be tested hierarchically as specified in Section 8.5. If all the testing preceding OS are statistically significant, OS in Ex11 ITT will be tested at 2-sided 0.05 significance level; if OS in Ex11 ITT is statistically significant, OS in AP ITT will be tested at 2-sided 0.05 significance level.

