3.4. Baseline

Unless specified otherwise, baseline measurements will be the most recent (i.e., last non-missing) value prior to receiving the first dose of study medication.

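### SAP 9.7 pools an absolute limit and a 20-unit change into one ECG outlier category for heart rate and PR, and counts wide QRS whatever the baseline, so the table cannot show what kind of abnormality occurred

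*SAP*

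**What the plan says.** SAP 9.7 (Electrocardiograms) first summarizes the ECG intervals and their changes from baseline by arm and scheduled visit. It then classifies patients:

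- **Low heart rate:** 50 bpm or less "bpm and/or decrease from baseline" of at least 20 bpm.
- **High heart rate:** 120 "bpm and/or increase from baseline" of at least 20 bpm, the 120 being a lower bound.
- **PR:** 220 "ms and/or increase from baseline" of at least 20 ms, the 220 again a lower bound.
- **QRS:** 120 ms or more, with no reference to baseline.

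QTc is treated differently in the same paragraph. Absolute thresholds are applied "per their maximum post-baseline absolute QTc interval", and change thresholds form a separate set on the maximum change.

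The unit is the patient: "The number and percentage of patients in each category will be summarized for each treatment group". For heart rate, PR and QRS the SAP does not say which post-baseline ECG decides.

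Under SAP 3.4, "baseline measurements will be the most recent (i.e., last non-missing) value prior to receiving the first dose of study medication", so each change is measured against one value. Protocol 4.2 sets a numeric ECG limit for QTcF only. Its cardiac exclusions do not bar a slow rate, a long PR or a wide QRS as such. Protocol 9.8.6 (Safety Analysis) contains no ECG analysis that would settle the rule.

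**The concern.** Read literally, *and/or* is an inclusive or, and three different patients land in the same cell:

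- heart rate 85 to 65 bpm: normal to normal, counted as low because the fall is 20;
- heart rate 65 to 48 bpm: a new crossing of the limit, with a fall of 17;
- heart rate 50 bpm before and after dosing: no change, counted as low.

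PR has the same problem: a patient at 225 ms throughout is counted. QRS shares the baseline part for a different reason, since it has an absolute limit only.

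Comparing the safety profiles of the two drugs is a stated objective (Protocol 2.2.2, SAP 2.1.3), and ECG change is a safety endpoint (Protocol 9.2.2.2.1). An outlier table exists to show individual abnormalities that averages hide. If its cells mix the three kinds of patient, a reader cannot tell what a count, or a difference in counts, means. A programmer who took *and/or* to mean *and* would produce a very different table from the same data.

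**Working it through.** **The plan's own figures.** The SAP gives no expected outlier frequency. The nearest figure that can be checked is the 262 PFS events, because the same medians (9 and 6 months, SAP 2.3) govern time on treatment and so the number of ECGs. Schoenfeld: 4 × (1.960 + 1.282)² / (ln 0.667)² = 42.03 / 0.164 = 257 events, 1.9% below 262; Freedman gives 264. The planning figure reproduces.

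**Number of ECGs.** Protocol Table 1 schedules an ECG on Day 1 of every cycle and at end of treatment, in both arms. Cycles last 42 days (SAP 2.2.2). At the medians, 9 × 30.4375 / 42 = 6.5 and 6 × 30.4375 / 42 = 4.3, so about 6 and 4 on-treatment ECGs before the end-of-treatment one.

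**One ECG, no drug effect.** The documents give no heart-rate distribution. Assume mean 72 bpm, between-patient SD 11 and within-patient SD 7, with independent normal errors.

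- Change limb: SD of a difference = √2 × 7 = 9.90; 20 / 9.90 = 2.02; one-sided tail 2.2%. At within-patient SD 5 it is 0.2%; at SD 9, 5.8%.
- Limit limb: total SD = √(11² + 7²) = 13.04. P(≤50) from (50 − 72) / 13.04 = −1.69 is 4.6%. P(≥120) from (120 − 72) / 13.04 = 3.68 is about 0.01%.

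So the high category is almost wholly the change limb (2.2% against 0.01%). The low category mixes two limbs of similar order (2.2% and 4.6%).

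**Several ECGs, no drug effect.** Simulation with 200,000 patients per setting; a patient counts if any post-baseline ECG qualifies:

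| Category | 4 ECGs, SD 7 | 6 ECGs, SD 7 | SD 5 to 9 |
|---|---|---|---|
| Low, either limb | 16% | 20% | 8–34% |
| Low, both limbs | 1.6% | 2.2% | 0.2–6.5% |
| High, either limb | 6.9% | 9.2% | 0.8–21% |
| High, both limbs | at most 0.1% | at most 0.1% | at most 0.1% |

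**Other assumptions.** A second simulation used heart-rate mean 75 and between-patient SD 10, PR mean 160 ms and between-patient SD 20, and within-patient SDs of 6 to 10. Time on treatment was exponential with medians of 9 and 6 months, capped at 24 months, and the end-of-treatment ECG was included. Mean ECGs were 8.4 and 6.4. Across both arms, the either-limb counts were 8.5–36.6% (low), 4.1–28.3% (high) and 4.5–28.8% (PR). Requiring both limbs gave 0.5–8.1%, at most 0.35% and at most 0.68%.

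**Unchanged baseline abnormality.** In the second simulation, patients at or below 50 bpm at baseline and flagged again were about 1 to 2.3%; for PR at or above 220 ms, about 0.2%. Under the mean-72, SD-7 assumptions the share cannot exceed the 4.6% who start at or below 50. QRS was not modelled.

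**Effect of visit count.** In the second simulation the longer-treated arm showed about 1 to 5 percentage points more flagged patients with no drug effect. In the first, going from 4 to 6 ECGs multiplies the low count by 20/16 = 1.25 under either limb and by 2.2/1.6, about 1.4, when both are required.

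**The case against.** **The table is supplementary and descriptive.** SAP 9.7 also gives intervals and changes by visit, and SAP 9.6 does so for heart rate. Those summaries do not grow with the number of ECGs and would show a systematic shift. Nothing in the testing hierarchy of SAP 8.5 depends on the outlier counts. All of this stands and keeps the point small.

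**The sizes are assumed.** The SDs are not in the documents. Protocol 6.11.4 requires at least 15 minutes supine or semi-recumbent, a pre-dose recording and central over-reading, which should limit visit-to-visit variation. The lower end of the ranges therefore deserves weight. A reader might infer that the counts will be mainly noise; the documents do not establish that.

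**A broad screen may be intended.** SAP 9.8 also joins an absolute LVEF range and a change by *or*. An inclusive screen is defensible, but it needs its components shown if the count is to be interpreted.

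**Requiring both limbs is not the obvious cure.** A reader might infer that *and/or* should simply become *and*. That would drop heart rate 65 to 48 (newly below the limit), 85 to 118 (a rise of 33) and PR 180 to 215 ms (a rise of 35). It would also leave the high heart-rate row nearly empty. Each limb carries information of its own.

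**Exposure is a separate matter.** A reader might infer that the wording biases the table against ripretinib. It does not: any patient-level ever-met count rises with the number of ECGs, including the QTc maxima, and the ratio persists when both limbs are required. That ripretinib will have more ECGs follows only from the planning medians, and the link assumes an any-or-worst-value rule that SAP 9.7 leaves unstated for these categories.

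**Conclusion.** The point holds as a cheap improvement to one descriptive safety table. SAP 9.7 pools two different criteria for low heart rate, high heart rate and PR, and applies no baseline condition to the limits or to QRS. No other section resolves this.

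With no drug effect and assumed within-patient SDs of 5 to 9 bpm, the pooled low category would hold about 8 to 34% of patients and the high category about 1 to 21%, the latter almost entirely from the change limb. These ranges also assume the heart-rate mean and between-patient SD above, independent errors and counting on any post-baseline ECG. Unchanged baseline abnormality is the smaller contributor for heart rate and PR; its size for QRS is not known from the documents.

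No hypothesis test or efficacy result is affected. The documents do not support a claim that *and/or* itself creates an imbalance between arms.

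**What to change.** In SAP 9.7, replace each pooled heart-rate and PR category by three labelled rows:

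- (a) limit met post-baseline and not met at baseline;
- (b) change from baseline of at least 20 bpm or 20 ms in the stated direction;
- (c) limit and change both met at the same ECG.

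Count QRS of 120 ms or more as on-treatment only if it was below 120 ms at baseline. Base every row on the worst post-baseline value, as the paragraph already does for QTc. Because each patient has one baseline, the lowest heart rate is also the largest fall (and the highest value the largest rise), so all three rows come from the same ECG.

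Rows (a) and (b) will still contain chance findings. The gain is that a reader can see which kind, and row (c) isolates the patients least likely to be fluctuation. The rows do not remove the dependence on number of ECGs, so any arm difference should be read beside exposure.

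Cost: one paragraph of the SAP and a few more table rows. No new data are needed.
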